3.1.1 Inclusion criteria

Pregnant women who meet the standers below will be included in this study.

3.1.1.1 The mother's age is 20 ~ 45 years old, the gestational age is 6 ~ 12 weeks, and

the ultrasound confirms that it is an intrauterine single or multiple pregnancy, and the weight loss is less than 10% compared with before pregnancy.;

3.1.1.2 Women diagnosed with moderate to severe NVP in the first trimester: the

severity of NVP was determined by the PUQE score (see Table 1), and the PUQE score ranged from 3 ~ 15, < 6 was mild NVP, 6 ~ 12 was moderate NVP, and ≥ 13 was severe NVP. PUQE score ≥ 6 may be included in this study;

3.1.1.3 Women voluntarily sign the informed consent form.

Table 1 Quantification of NVP in the US ACOG guidelines

1. In general, how often do you feel nauseous or nauseous each day?				
Never (1)	≤ 1 h (2)	2~3 h (3)	4~6 h (4)	> 6 h (5)
2. In general, how many times a day do you vomit?				
Never (1)	1~2 (2)	3~4 (3)	5~6 (4)	≥ 7 (5)
3. In general, how many times a day do you retch (no contents) ?				
Never (1)	1~2 (2)	3~4 (3)	5~6 (4)	≥ 7 (5)

Total score (add all the points together): Mild NVP: < 6 , moderate NVP: $6 \sim 12$, severe NVP: ≥ 13

3.1.2 Exclusion criteria

Pregnant women who meet any of the following conditions will not be included.

3.1.2.1 Age < 20 years, or > 45 years.

3.1.2.2 Gestational age < 6 weeks, or > 12 weeks.

3.1.2.3 PUQE score < 6 .

3.1.2.4 frequent nausea and vomiting, weight loss of $> 10\%$ compared with before pregnancy; or symptoms such as listlessness, paleness, dry skin, sunken eye sockets, and a marked decrease in urine output (less than 400ml of urine in 24 hours or less than 5 times and a small amount of urine in 24 hours).

3.1.2.5 At rest, body temperature > 38 °C, systolic blood pressure < 90 mmHg or > 140 mmHg, diastolic blood pressure < 60 mmHg or > 90 mmHg, heart rate ≥ 100 beats per minute, or oxygen saturation $< 95\%$.

3.1.2.6 Urinalysis: urine ketones: +++ and above; or (and) urine protein: ++ and above.

3.1.2.7 Blood biochemistry: serum potassium ≤ 3.0 mmol/L, serum sodium ≤ 130 mmol/L; or abnormal liver function: elevated liver enzymes ≥ 2 times the upper limit of normal; or renal dysfunction: elevated serum creatinine and urea nitrogen.

3.1.2.8 Other digestive diseases that cause nausea and vomiting, such as gastrointestinal infections (with diarrhea), gastric ulcers (with epigastric pain

or hematemesis), cholecystitis, biliary roundworms, pancreatitis (with abdominal pain, plasma amylase levels rise to 5 ~ 10 times normal), viral hepatitis (positive hepatitis virology, liver enzyme levels $\geq 1\ 000\ \text{U/L}$) or acute fatty liver during pregnancy, tumors of the digestive tract.

3.1.2.9 Suffering from immune diseases such as systemic lupus erythematosus, scleroderma, dermatomyositis, IgG4-related diseases, immune nephropathy, etc.

3.1.2.10 Have uncorrected diseases of the endocrine system, such as diabetes, Addison's disease, hyperthyroidism, hypothyroidism, thyroid tumors, adrenal tumors, etc.

3.1.2.11 Suffering from neurological diseases such as migraine, neuromyelitis optica, epilepsy, and neurologic tumors.

3.1.2.12 In the past 1 week, have taken antiemetic drugs such as ondansetron, metoclopramide (metoclopramide), promethazine, and anti-vomiting Chinese medicine.

3.1.2.13 Monoamine oxidase inhibitors are used.

3.1.2.14 Had TN treatment in recent 3 months.

3.1.2.15 Unwilling to sign the informed consent of this study.

3.2 The intervention program

According to the theory of traditional Chinese medicine, the treatment plan of TN is formulated, and the study protocol follows the CONSORT and STRICTA regulations, and details the number of TN used, the frequency of treatment and the duration of treatment. Both the TN group and the sham TN group were treated with a fixed treatment regimen, which was treated once every 3 days, for a total of 5 treatments for 15 days. During the same period, the blank control group was not given TN or sham TN treatment. All three groups of patients were given pregnancy care and dietary guidance.

3.2.1 Protocol for TN group

The main acupoints of treatment are Zhongwan (CV12), bilateral Neiguan (SP6), and

bilateral Zusani (ST36), with a total of 5 acupoints. Patients with Qi stagnation should be given Danzhong (CV17) or the Ashi acupoint (Identify the most prominent tender point between the Danzhong (CV17) and Zhongwan (CV12). If such a tender point exists, apply a TN at the tender point, that is, the Ashi acupoint. If no tender point is found, apply the TN at the Danzhong acupoint. Just choose one of the two.), patients with liver and stomach disharmony should be given bilateral Geshu (BL17), patients with phlegm-dampness obstruction should be added bilateral Fenglong (ST40), and patients with weak spleen and stomach should be added bilateral Weishu (BL21). The above acupoints are treated with TN.

The doctor disinfects his hands, strictly disinfects the local skin of the acupoint, applies the disposable sterile TN to the sterilized acupoint, and after a slight pressure, removes the isolation paper (the function of the isolation paper is to avoid direct contact with the sterile glue surface when adhering it to the skin), and press again to ensure that the TN stick the surface of the acupoint firmly. The TN will be kept in the acupoints for 3 days. During the 3-day retention of TN, the patient presses the TN 3 times a day and half a minute per time per acupoint. After 3 days retention of TN, the patient will be instructed to go to the hospital, where the doctor will remove the TN, disinfect the local skin of acupoints and conduct the next treatment of TN. A total of 5 sessions treatment will be applied for a duration of 15 days.

3.2.2 Protocol for sham TN group

The sham TN will be used for the sham TN group. Even though the appearance and shape of sham TN are similar to the real TN, the sham TN has no needle body. Therefore, the sham TN does not produce a needle-like effect of TN

The acupoints of sham TN group are the same as those of TN group. The use of sham TN was the same as that of the TN group. After 3 days retention of sham TN, the patient was instructed to go to the hospital, where the doctor removed the sham TN, and conducted the next treatment after local skin disinfection. A total of 5 treatments were given for a duration of 15 days.

3.2.3 Record for the treatment

The treatment date, time and the name of the acupuncturist are recorded when the patient receives TN or sham TN treatment. No treatment is given to the blank control group, but the date and times of the inquiry of blank control group are also recorded. During the treatment, the local hematoma or turquoise, pain or skin allergies that may occur during the treatment, as well as other discomforts after the treatment (nausea, vomiting, palpitations, dizziness, headache, anorexia and insomnia), should be recorded in detail and disposed in time.

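### The protocol foresees skin allergy from an adhesive device applied five times for 3 days, but no eligibility criterion screens for known adhesive or needle-metal allergy or for damaged skin at a treatment point

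*Protocol*

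**What the plan says.** Section 3.2.3 names "the local hematoma or turquoise, pain or skin allergies that may occur during the treatment" and asks that such events "should be recorded in detail and disposed in time". It gives no rule for withdrawing a woman who reacts.

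Section 3.2.1 fixes the exposure: "The TN will be kept in the acupoints for 3 days", and "A total of 5 sessions treatment will be applied for a duration of 15 days". The device is held on by glue; the isolation paper is there to "avoid direct contact with the sterile glue surface when adhering it to the skin". The patient also presses each point three times a day.

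Section 3.2.2 repeats this for the sham: "The acupoints of sham TN group are the same as those of TN group", and it is used in the same way, except that "the sham TN has no needle body". Under section 3.2 the blank control group wears no device.

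Section 3.1.2 opens with "Pregnant women who meet any of the following conditions will not be included" and lists fifteen conditions. They cover age, gestation, severity, vital signs, laboratory values, other diseases, drugs, recent TN treatment and refusal of consent. The inclusion criteria in 3.1.1 cover age, gestation, ultrasound findings, weight loss, PUQE score and consent.

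**The concern.** The protocol anticipates a device reaction in one section and does not screen for its obvious predictors in another. A woman who already knows that she reacts to plasters, or who has damaged skin over a treatment point, meets no exclusion. She can be assigned to repeated wear at that point. This is first a matter of protecting pregnant participants, and eligibility has to be settled in the protocol itself.

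There is also a statistical side. Device reactions can occur only where a device is worn. If some women stop because of the adhesive, that stopping falls on TN and sham but not on blank control, and section 3.6.2 compares the PUQE change among all three groups. Needle-related reactions concern TN alone and could make TN and sham differ in adherence. Predictable reactions would also feed into the adverse-event proportions tested in section 3.5.

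**Working it through.** **1. Eligibility against expected reactions**

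| Hazard | Foreseen? | Arms exposed | Criterion in 3.1.1 or 3.1.2 |
|---|---|---|---|
| Adhesive allergy | Skin allergy, 3.2.3 | TN and sham | None |
| Needle-metal allergy | Skin allergy, 3.2.3 | TN only (sham has no needle) | None |
| Damaged skin at a treatment point | Not named | TN and sham | None |
| Local haematoma from puncture | 3.2.3 | TN only | None |

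The nearest entries are 3.1.2.9, which names scleroderma and dermatomyositis as immune diseases, and 3.1.2.14, recent TN treatment. Neither addresses tolerance of the device.

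**2. Exposure per woman in a device arm** (section 3.2.1)

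Placements = points per session × 5 sessions.
- Main points only: 5 × 5 = 25.
- One pattern, adding 1 or 2 points: 6 × 5 = 30, or 7 × 5 = 35.
- All four patterns, adding 1 + 2 + 2 + 2 = 7 points: 12 × 5 = 60.

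The protocol does not say how many patterns a woman has, so the range is 25 to 60. Each placement lasts 3 days.

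**3. How many women might be concerned**

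The documents give no prevalence of sensitivity and no reaction or withdrawal rate. Assume that 2% to 5% of women are known to be adhesive-sensitive: 0.02 × 160 = 3.2 and 0.05 × 160 = 8, so about 3 to 8 in each device arm. A similar number in the blank arm would not be exposed. This is a count of sensitive women. It caps the number who could stop for this reason; it does not estimate it.

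**4. Effect on power for TN versus sham**

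The plan's own figure first. Inputs from 3.6.1: changes of 4.9 and 4.0, so δ = 0.9; SDs of 2.4 and 2.7; two-sided α = 0.05; power 0.80.
- s² = (2.4² + 2.7²)/2 = 6.525, so s = 2.554.
- n = 2 × (1.960 + 0.842)² × 6.525 / 0.9² ≈ 126.5, rounded up to 127. The t-test version gives 127.4, rounded up to the stated 128.
- 128 / (1 − 0.20) = 160, as stated.

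Now let a further share x of each device arm be lost, leaving 160 × (1 − 0.20 − x):

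| Extra loss x | Evaluable per arm | Power |
|---|---|---|
| 0% | 128 | 80.5% |
| 2% | 125 | 79.5% |
| 5% | 120 | 77.9% |
| 10% | 112 | 75.1% |

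The table treats every such woman as having no outcome. Power is hardly affected at 2% to 5%. The table says nothing about bias from unequal stopping.

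**5. Where unequal stopping would enter** (section 3.6.2)
- Intention-to-treat: women stay in, and missing PUQE scores are multiply imputed assuming missing at random.
- Modified intention-to-treat: women without the primary measurement drop out.
- Per-protocol set: women who stop the device drop out.
- Adherence and satisfaction (3.3.2.7, 3.3.2.8) and adverse-event proportions (3.5) are affected directly.

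**6. Bleeding**

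The background section says the needle, 1.2 to 2.5 mm long, does not injure blood vessels. Section 3.2.3 lists local haematoma as possible. The two statements do not agree.

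**The case against.** Listing a possible reaction does not contradict the exclusion list. A sponsor may reasonably admit women with mild sensitivities and record what happens. A woman who knows she reacts to plasters can decline, and the consent pages, which may carry a warning, are not available here. This stands in part: the criteria leave such women eligible but do not oblige a site to enrol them. With fourteen sites, though, leaving the matter to individual judgement invites uneven screening.

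A reader might infer that these women will stop early and be lost from the two device arms only, biasing the trial's main result. The documents do not support that. No section says that a woman who reacts leaves the study, and stopping the device is not the same as losing the PUQE score. The primary analysis keeps all women by intention-to-treat. Adhesive contact is the same in TN and sham, so adhesive-related loss should be roughly balanced in the comparison that was sized.

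A reader might also treat all the hazards as common to both device arms. They are not: the sham shares the adhesive but not the needle. Nor is one needle worn for 15 days; there are five successive 3-day applications.

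Finally, the haematoma statement conflicts with the background, so it is too weak a basis for drafting an exclusion for bleeding disorders. That objection stands.

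**Conclusion.** The gap is real and worth closing: skin allergy is foreseen, adhesive wear is repeated in two arms, and no entry criterion covers known adhesive or needle-metal allergy or damaged skin at a treatment point. The main ground is participant safety. The statistical consequence is possible, not shown. It concerns comparisons with blank control, the per-protocol set, adherence and adverse-event proportions, and, for needle-related reactions, TN versus sham. Its size is unknown; the 3 to 8 women per arm rest wholly on an assumed 2% to 5% prevalence. A material loss of power for the primary comparison is not supported. On bleeding tendency, the documents justify only a request to reconcile two statements.

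**What to change.** Add to section 3.1.2 a criterion covering known allergy to adhesive or to the needle metal, and damaged skin at any possible treatment point, with the exact clinical wording set by the sponsor. Check it by history and by inspecting the acupoints before randomisation, and apply it identically to all three groups, including the metal item, so that the groups stay comparable.

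Separately, reconcile the background statement on blood vessels with the haematoma listed in 3.2.3. The sponsor can then decide whether bleeding tendency needs an eligibility criterion.

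The cost is one protocol line, a screening question and a skin inspection. A few women would be lost to recruitment, and no new test is needed.

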3.3 Outcome measures

3.3.1 Primary outcome measure

PUQE scores were evaluated before treatment and on days 3, 6, 9, 12, and 15 of treatment. The primary outcome measure was the change of PUQE score on day 15 at the end of the treatment when compared with the baseline.

3.3.2 secondary efficacy endpoints

3.3.2.1 Questionnaires

Evaluation is performed before and after treatment.

3.3.2.1.1 Quality of life survey: The NVP Quality of Life questionnaire (NVPQOL) is used to evaluate the quality of life of pregnant women.

3.3.2.1.2 Anxiety and depression status survey: Zung anxiety self-rating scale (Zung-SAS) and Zung depression self-rating scale (Zung-SDS) are used to evaluate the anxiety and depression status.

3.3.2.1.3 Sleep status survey: The Pittsburgh sleep quality index (PSQI) was used to survey the sleep status of patients.

3.3.2.2 changes in the patient's weight; changes in electrolytes (sodium, potassium, chloride, magnesium, calcium, iron, and zinc) in the blood; arterial blood gas analysis; changes in liver and kidney function; Changes in thyroid function.

3.3.2.3 Situation of intravenous fluid therapy, use of additional medications, hospitalization, and termination of pregnancy.

3.3.2.4 Pregnancy complications, including miscarriage (first and second trimester), hypertensive disorders during pregnancy, and gestational diabetes.

3.3.2.5 Pregnancy outcomes, including termination of pregnancy and delivery outcomes (including live birth, vaginal birth, caesarean section, gestational age, etc.)

3.3.2.6 Neonatal outcomes, including preterm birth, birth weight, and small for gestational age (SGA). "Small gestational age" refers to babies with birth weight below the 10th percentile according to the sex and gestational age of the Chinese population.

3.3.2.7 Patient's satisfaction with treatment.

3.3.2.8 Patient's adherence to treatment.

3.4 Follow-up

After 15 days of the treatment, participants will be followed up once a week for a total of 4 weeks, and then once a month until live birth.

3.5 Safety assessment

Adverse events will be classified, and the percentage of adverse events and severe adverse events occurred during treatment will be recorded in detail. Chi-square test is used to analyze the total proportion of adverse events in each treatment regimen and the differences between the classifications. Unless otherwise formally requested, each data safety oversight board report will report details and summaries of adverse events in a double-blind manner.

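### Section 3.5 counts adverse events only during the 15 days of treatment, although women are contacted until birth; late local reactions and unlisted late serious events have no stated count, and the later pregnancy outcomes are not tied to the safety assessment

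*Protocol*

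**What the plan says.** Section 3.5 of the protocol is its only safety section. It sets the count: "the percentage of adverse events and severe adverse events occurred during treatment will be recorded in detail". It then gives the analysis: "Chi-square test is used to analyze the total proportion of adverse events in each treatment regimen and the differences between the classifications". A last sentence says that the data safety oversight board receives details and summaries of adverse events in blinded form.

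The treatment period is fixed in section 3.2.1: "A total of 5 sessions treatment will be applied for a duration of 15 days". Section 3.2.2 gives the sham group the same schedule. Women enter when "the gestational age is 6 ~ 12 weeks" (section 3.1.1.1).

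Contact does not stop with treatment. Under section 3.4, after the 15 days, "participants will be followed up once a week for a total of 4 weeks, and then once a month until live birth".

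Later events are dealt with elsewhere, under the heading of secondary efficacy endpoints (section 3.3.2):

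- 3.3.2.3 covers hospitalization, termination, intravenous fluids and additional medication, without a stated time window.
- 3.3.2.4 reads "Pregnancy complications, including miscarriage (first and second trimester), hypertensive disorders during pregnancy, and gestational diabetes".
- 3.3.2.5 begins "Pregnancy outcomes, including termination of pregnancy and delivery outcomes" and goes on to live birth, mode of delivery and gestational age.
- 3.3.2.6 names birth weight, preterm birth and SGA.

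Section 3.6.2 assigns a chi-square test to secondary outcomes that are counts.

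**The concern.** Section 2 makes the evaluation of safety one of the trial's objectives, and the women are treated in early pregnancy. For such a trial the length of the adverse-event window is a matter for the protocol, because it decides what the sites write down. An analysis plan cannot recover events that sites were never asked to record. Here the window is stated, and it closes on the day the last device is removed, although the trial will go on speaking to each woman for months.

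At stake is how complete the safety conclusion can be. Followed as written, the adverse-event table would describe the treatment fortnight. The later pregnancy and neonatal outcomes would appear among the efficacy results, and a few kinds of later event would appear in neither place.

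**Working it through.** The plan gives no figure to reproduce on this point. The check compares the counting window with the scheduled observation, then sets the outcome lists beside the safety rule.

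**1. Length of the window**

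Inputs: treatment of 15 days (5 sessions × 3 days of retention = 15; section 3.2.1); entry at 6 to 12 weeks (section 3.1.1.1). Birth at 37 to 40 weeks is an assumption, since the protocol gives no figure for it.

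Days from entry to birth = (weeks at birth − weeks at entry) × 7. Share covered = 15 / days.

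| Birth (assumed) | Entry | Days to birth | Share covered | Days after window |
|---|---|---|---|---|
| 37 weeks | 6 weeks | 31 × 7 = 217 | 15/217 = 6.9% | 202 |
| 37 weeks | 12 weeks | 25 × 7 = 175 | 15/175 = 8.6% | 160 |
| 40 weeks | 6 weeks | 34 × 7 = 238 | 15/238 = 6.3% | 223 |
| 40 weeks | 12 weeks | 28 × 7 = 196 | 15/196 = 7.7% | 181 |

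The window closes at (6 × 7 + 15)/7 = 8.1 weeks to (12 × 7 + 15)/7 = 14.1 weeks of gestation. The fifth device is removed on day 15, so no time after the last removal lies inside the window.

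**2. What is captured after day 15**

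| Later event | Where collected | Linked to 3.5? |
|---|---|---|
| Miscarriage, hypertensive disorders, gestational diabetes | 3.3.2.4 | No |
| Hospitalization, termination | 3.3.2.3 (termination also 3.3.2.5), no stated time window | No |
| Live birth, mode of delivery, gestational age at delivery | 3.3.2.5 | No |
| Preterm birth, birth weight, SGA | 3.3.2.6 | No |
| Stillbirth | Not named; inferable as a pregnancy without live birth | No |
| Congenital anomaly, neonatal death | Not named | No |
| Local reaction first seen after the last removal | No stated count | Outside the window |
| Late serious maternal event that is neither a listed complication nor a hospitalization | No stated count | Outside the window |

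**3. Does section 3.2.3 fill the gap?**

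That section asks sites to record local reactions and also discomforts after treatment. Its sentence is framed as a record kept during treatment, and the later part can be read as after each session. It gives no end date, no serious-event category and no analysis. It therefore does not supply a post-treatment count.

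**The case against.** The strongest reply is that the harms that matter most are already prespecified. The lists in 3.3.2.3 to 3.3.2.6 cover the main obstetric and neonatal events, section 3.4 schedules the contacts needed to observe them, and section 3.6.2 compares counts with the same kind of test as section 3.5. The lists are also worded as open rather than closed. On this view only a labelling point remains.

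Most of that stands, and it rules out several stronger readings that a reader might infer:

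- *That later harms go unassessed.* The documents do not support this; most are collected and compared by group.
- *That the board will not see later events.* The time limit is in the sentence that sets the count. The sentences on the chi-square test and on the board reports carry no limit of their own. Exclusion from the reports is an inference; what can be said is that no link is stated.
- *That the protocol's own background calls for anomaly data on needling.* The fears of teratogenicity and birth defects described there concern drugs. They are no evidence of harm from a needle.
- *That more than 90% of harms would be missed.* The share computed above is of calendar time. Events caused by a local device may well cluster while it is worn.

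The reply does not remove the rest. An open list does not tell a site to record an anomaly or a neonatal death. A local reaction after day 15 falls outside a window that section 3.5 states in words. The efficacy heading leaves it undecided whether, for example, a second-trimester miscarriage belongs in the safety summary.

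**Conclusion.** The point holds in a limited form. Section 3.5 states a treatment-period window of 15 days, which leaves about 160 to 223 days of scheduled contact without an adverse-event count, if birth falls at 37 to 40 weeks. Over that time most important obstetric outcomes are collected, but as efficacy endpoints with no stated tie to the safety assessment. What has no stated count is late local reactions and late serious events that are not listed endpoints. Congenital anomaly and neonatal death are not named, and stillbirth is only inferable.

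The number of events affected cannot be estimated from the protocol, which gives no event rates. Neither the sample size nor the primary analysis is touched. This is an inexpensive improvement to the safety conclusion, not a flaw that undermines the trial.

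**What to change.** In section 3.5:

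1. Record adverse events from the first application through the four weekly follow-up contacts, and serious adverse events through the monthly contacts to the end of pregnancy, however it ends. For the blank control group, start from the matching date. The protocol's term is severe; say whether serious is meant.
2. Name stillbirth, congenital anomaly, and neonatal death known at the birth contact.
3. Cross-refer the outcomes of 3.3.2.3 to 3.3.2.6 as safety outcomes, tabulated by group and included in the board reports.

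The adverse-event window then becomes 15 + 28 = 43 days, and serious events are covered for the whole scheduled follow-up.

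The cost is a few fields on forms for contacts already planned, some added data entry, and more background pregnancy events to classify. No new visits are needed. One limit remains: section 3.4 ends follow-up at live birth, so neonatal deaths after the birth contact would still be missed, and the report should say so.

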RCTs are still needed to provide high-quality evidence-based evidence. This project intends to use multi-center, large-sample, randomized, controlled, double-blind clinical trials to observe the effects of nausea and vomiting, quality of life, anxiety and depression, weight change, blood electrolyte levels, liver and kidney function, thyroid function, intravenous infusion therapy, use of additional drugs, hospitalization, pregnancy complications (gestational diabetes and hypertensive diseases), pregnancy outcomes and neonatal outcomes in women with VNP, and evaluate their safety, so as to provide high-quality evidence support for the clinical promotion and application of needles in the treatment of VNP.

2. Study objectives

A multicenter, large-sample, randomized, controlled, double-blind clinical trial was conducted to observe the effects of TN on nausea and vomiting, quality of life, anxiety and depression, weight change, blood electrolyte levels, liver and kidney function, thyroid function, intravenous fluid therapy, use of additional drugs, hospitalization, pregnancy complications, pregnancy outcomes, and neonatal outcomes in women with VNP, and to evaluate its safety.

3. Study content

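### Adverse-event recording is tied to the 15-day treatment, so local reactions after the last removal and some late severe events have no stated recording, although contacts run to birth

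*Protocol*

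**What the plan says.** Evaluating safety is part of the stated objective: section 2 sets out to study the thumbtack needle (TN) "in women with VNP, and to evaluate its safety".

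Three places bear on when events are recorded:

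- **Protocol 3.5** fixes the period: "the percentage of adverse events and severe adverse events occurred during treatment will be recorded in detail". The next sentence gives the comparison: "Chi-square test is used to analyze the total proportion of adverse events in each treatment regimen". It names no period of its own.
- **Protocol 3.2.3** covers local reactions (haematoma or bruising, "pain or skin allergies that may occur during the treatment"). It then adds a second group: "as well as other discomforts after the treatment (nausea, vomiting, palpitations, dizziness, headache, anorexia and insomnia". No end date is given for that group.
- **Protocol 3.4** continues contact after day 15, weekly for four weeks and then monthly up to live birth. It does not say that adverse events are asked about.

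The length of treatment comes from 3.2: patients are "treated once every 3 days, for a total of 5 treatments for 15 days". Section 3.2.1 adds the removal step: "After 3 days retention of TN, the patient will be instructed to go to the hospital, where the doctor will remove the TN".

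**The concern.** The devices are worn in sets for 3 days at a time, and the last set comes off when the recording period closes. A skin or puncture-site reaction can first show after a device is removed. For the first four sets, such a reaction still falls inside the treatment period. For the fifth set it does not.

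The same wording covers severe adverse events. A severe event after day 15 is captured only if it happens to be one of the endpoints in 3.3.2.

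What is at stake is the completeness of the safety comparison. Late local reactions can arise only where a device was worn, so leaving them out would tend to lower the count in the TN and sham arms relative to the blank arm. Sites collect what the protocol tells them to collect, and an event nobody asked about is hard to recover at the analysis stage.

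**Working it through.** The protocol states no figure that can be reproduced here, so the check sets the sections side by side and then does simple arithmetic on the periods.

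**1. Where the treatment period ends.** From 3.2 and 3.2.1: 5 sessions × 3 days = 15 days. Counting from the first application, removals fall on days 3, 6, 9, 12 and 15.

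**2. Recording time left after each removal.** 15 − 3k for k = 1 to 5 gives 12, 9, 6, 3 and 0 days. Only the fifth set has none.

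**3. How much exposure the fifth set represents.** Section 3.2.1 gives main points "with a total of 5 acupoints". A syndrome pattern adds 1 device (CV17 or the tender point) or 2 (bilateral BL17, ST40 or BL21). Assuming at most one added pattern per woman:

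- per session: 5 + 0 to 5 + 2 = 5 to 7 devices
- per course: 5 × 5 to 5 × 7 = 25 to 35 devices
- share of the last session: 1/5 = 20%
- in an arm of 160 (section 3.1): 160 × 5 = 800 to 160 × 7 = 1,120 devices, and the same in the sham arm, which uses the same points.

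These are devices without recording time after removal. They are not missed events.

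**4. What missed events could look like.** The protocol gives no rate of late local reactions. The rates below are assumptions, to show scale only, for one arm of 160.

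| Assumed share of women with a first local reaction after the last removal | Expected women, 160 × rate | Chance of at least one, 1 − (1 − rate)^160 |
|---|---|---|
| 0.5% | 0.8 | 55% |
| 1% | 1.6 | 80% |
| 2% | 3.2 | 96% |
| 5% | 8.0 | >99.9% |

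The true rate could be close to zero.

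**5. Share of follow-up covered.** Entry is at 6 to 12 weeks (3.1.1.1). Assuming birth at 40 weeks, follow-up from entry is 34 × 7 = 238 days to 28 × 7 = 196 days. The 15-day window is 15/238 = 6.3% to 15/196 = 7.7% of it. Recording through the fourth weekly contact (15 + 28 = 43 days) would cover 43/238 = 18% to 43/196 = 22%.

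**6. Contacts available after day 15.** There are 4 weekly contacts. Monthly contacts after day 43, with 30-day months and birth assumed at 37 to 40 weeks:

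- entry at 6 weeks: (31 × 7 − 43)/30 = 5.8 to (34 × 7 − 43)/30 = 6.5
- entry at 12 weeks: (25 × 7 − 43)/30 = 4.4 to (28 × 7 − 43)/30 = 5.1

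That is 4 to 6 complete months, so about 8 to 10 contacts in all.

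**7. What other sections already catch.** Section 3.3.2 collects intravenous fluids, additional medication, hospitalization, termination, miscarriage, hypertensive disorders, gestational diabetes, delivery outcomes, preterm birth, birth weight and small for gestational age. What is left over is a late local reaction and a severe event outside these headings. An example of the latter is a severe skin infection treated without admission, where at most the extra medication would show.

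**The case against.** The strongest case against has five parts.

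- **The text does not say that nothing else is recorded.** The opening of 3.5 has adverse events classified without naming a period, and the chi-square and safety-board sentences are equally open. The treatment-period wording could be read as defining a summary percentage. This is fair as far as it goes: a reader should not infer that later recording is barred. But the only period the protocol states is the treatment period, and nothing instructs a site to go further.
- **Section 3.2.3 already reaches past treatment.** The symptoms in its list are all systemic, but they follow directly on the local reactions and could be read as examples. That may cover part of the gap. However, the sentence sets no end date, and the phrase can mean after each session or after the course, so sites could apply it differently.
- **Most late severe events surface in 3.3.2.** This stands. It is tempting to infer that miscarriage, termination or admissions after day 15 go uncollected; they do not. The complication, delivery and neonatal lists are also worded as open lists, so even an item they do not name, such as congenital anomaly, cannot be said to be excluded.
- **The last removal is a hospital visit.** It coincides with the day-15 assessment, so reactions present then fall within the period. This also stands, and confines the first gap to reactions that appear later.
- **The longer window adds noise.** Events of pregnancy itself would enter all arms and could blur the device comparison. This is a good reason to keep the treatment-period percentage as a separate figure, but not a reason to leave the later events unrecorded.

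Nor can the point be left to a statistical analysis plan. The collection period is an instruction to sites, the protocol has fixed it, and an analysis plan cannot restore events that were not collected.

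**Conclusion.** The point holds in a narrow form. As written, the protocol has no stated recording for a local reaction that first appears after the fifth removal at about day 15, or for a late severe event that the 3.3.2 endpoints do not capture, although contacts to birth are already planned.

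The size is unknown from the document. The firm figures are that the fifth set has 0 days of recording after removal, against 12, 9, 6 and 3 for the earlier sets, and that it makes up 20% of devices. The figure of about 0.8 to 8 women per arm of 160 rests wholly on assumed rates of 0.5% to 5% and should not be read as an estimate. It would also be total loss only if the after-treatment clause in 3.2.3 covers no late local reactions.

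A reader might infer that the trial's safety conclusions are unsound or that late harms in general are ignored. The documents do not support that. No efficacy estimate or test is affected. This is a low-cost improvement to a stated objective, worth considering rather than essential.

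**What to change.** - **In 3.5**, record adverse events, including local reactions, from randomisation to the fourth weekly contact, and severe adverse events from randomisation to the end of pregnancy, using the contacts already scheduled in 3.4.
- **Keep the treatment-period percentage** and report it separately from the follow-up period, and say which period the chi-square comparison uses. The device comparison is then not mixed with later background events.
- **In 3.2.3**, give the local reactions and the other discomforts the same end date as adverse events in 3.5.

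The cost is a change of wording and one adverse-event question at about 8 to 10 planned contacts. It needs no new visits and no change to the sample size. The downside is more event records to process and more background pregnancy events in all three arms, which separate reporting by period and the concurrent controls keep interpretable. The fourth weekly contact is a practical cut-off that nothing in the protocol requires; another clearly stated date would serve.
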